Objectives: The objective of this study is to evaluate if enteral absorption improves in subjects with SBS following therapy with pancreatic enzymes. Enteral absorption will primarily be assessed using stool coefficient of fat absorption (CFA). Secondary objectives of the study include measurement of coefficient of nitrogen absorption (CNA) and stool bomb calorimetry (BC) before and after pancreatic enzyme administration. A subset of subjects will also have enteral absorption measured using the malabsorption blood test (MBT) before and after pancreatic enzyme administration.

Study Design: This is an interventional study of subjects with SBS who will be evaluated before and after pancreatic enzyme administration. A subset of subjects will have the MBT performed before and after pancreatic enzyme administration as a measure of enteral fat absorption.

Setting/Participants: This outpatient study will be conducted at CHOP. Approximately, sixteen subjects with SBS between the ages of 4.0 and 17.9 years and ten adult subjects with SBS between the ages of 18 and 75 years will be enrolled. Only adult subjects have the option to be part of the subset that has the MBT.

Study Interventions and Measures: Subjects with SBS will be evaluated both on and off Creon™, a pancreatic enzyme medication. Enteral absorption will be measured before and after pancreatic enzyme administration. Enteral absorption will be measured using three methods: CFA, CNA, and BC. A subset of adult subjects will also have the MBT before and after pancreatic enzyme administration. Subjects with SBS have significant malabsorption and have several proposed mechanisms of functional pancreatic insufficiency. The longterm goal is to determine if pancreatic enzymes improve enteral absorption in patients with SBS, it may allow parenteral nutrition to be weaned and improve both their morbidity and mortality.

PROTOCOL SYNOPSIS

Study Title	The Use of Pancreatic Enzymes in Short Bowel Syndrome
Funder	AbbVie Inc.
Clinical Phase	Phase II – This is an open-label intervention therapeutic exploratory study

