Finally, gastric acid hypersecretion may contribute to functional pancreatic insufficiency in patients with SBS. Gastric acid hypersecretion, specifically, tends to occur for months following intestinal resection. It is thought to be due to altered enteroendocrine hormone signaling following resection and a loss of inhibition of gastrin that leads to increased gastric acid production^{6,16,17}. The effect of gastric acid hypersecretion is two-fold in that it increases the volume of contents in the intestinal

lumen, which serves to dilute pancreatic enzymes present in the lumen. It also drives the luminal pH in the small bowel down, which results in suboptimal activity of pancreatic enzymes^{6,16,17}.

Our primary objective is to demonstrate that treating patients with SBS with pancreatic enzymes will improve enteral fat absorption. We will look to determine if administration of pancreatic enzymes in these subjects with SBS results in a change in CFA, as well as other markers of absorption, including stool bomb calorimetry and coefficient of nitrogen absorption (CNA).

An exploratory aspect of this study includes the use of the malabsorption blood test (MBT) as a measure of enteral absorption. Clinically, it is challenging to measure absorption in patients with SBS and this is typically estimated by monitoring height, weight, and serum micronutrient levels. This study will be one of the first to perform multiple measures of absorption on patients with short bowel syndrome. Currently, the gold standard for gut absorption is the CFA. The MBT will be utilized on a subset of subjects in this study as an additional measure of enteral fat absorption, but also to characterize the degree of pancreatic insufficiency in subjects. In this test, subjects consume a high fat shake that contains pentadecanoic acid (PA), a free fatty acid, and triheptadecanoic acid (THA), a triglyceride. Baseline serum levels of PA and THA are measured and then serial serum levels are checked following consumption of the shake allowing calculations to determine enteral fat absorption to be made. The MBT is unique in that it measures absorption of both a triglyceride and a free fatty acid. Improved pancreatic function should result in improvement of triglyceride absorption specifically, as absorption of free fatty acids does not depend upon lipase.

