3.2 Allocation to Treatment Groups and Blinding

This is an open-label intervention therapeutic exploratory study, and not a randomized controlled trial.

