5.2 Efficacy

5.2.2. Diagnostic tests, Scales, Measures

Coefficient of fat absorption (CFA): The coefficient of fat absorption (CFA %) will be calculated based on a 72 hour stool and a 3-day weighed diet record collection performed after both Study Visit #1 and #2. Collection of stool will begin 24 hours after dietary records are started. All subjects will remain on their normal diet during stool collection. This includes the normal meals, snacks, and tube feeds that they typically receive. All subjects will receive a home collection kit and detailed instructions on stool collection. Stool collections will be performed at home and returned to CHOP upon completion. Subjects who are in diapers can either use plastic wrap to line the diaper or a urine collection bag secured around the anus for stool collection. They will then transfer stool from the plastic wrap or the collection bag to a stool collection container. All materials, including hand gloves, will be provided to ensure safe and accurate stool collection. All stool will be frozen until the time of analysis. Total fat content of the stool will be determined by a gravimetric method (Mayo Medical Laboratories, Rochester, MN). Total dietary intake of fat will be determined from the 3-day weighed food records. CFA % will be calculated based on determining the grams of fat consumed and the grams of fat excreted²⁷. CFA % will be compared for each subject before and after administration of pancreatic enzymes.

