Coefficient of nitrogen absorption (CNA): The coefficient of nitrogen absorption (CNA %) will be calculated based on a 72 hour stool and a 3-day weighed diet record collection performed both at Study Visit #1 and #2. Collection of stool will begin 24 hours after dietary records are started. All subjects will remain on their normal diet during stool collection. This includes the normal meals, snacks, and tube feeds that they typically receive. Subjects will receive materials and instructions for proper stool collection. All samples will be collected at home and returned to CHOP. Stool will be frozen until the time of analysis. Total nitrogen content of stool will be determined by a gravimetric method (Mayo Medical Laboratories, Rochester, MN). Total dietary intake of nitrogen will be determined from a 3-day weighed food record. CNA % will be calculated based on grams of nitrogen consumed and grams of nitrogen excreted²⁷. CNA % will serve as a measure of protein absorption. CNA % will be compared for each subject before and after administration of pancreatic enzymes.

Bomb calorimetry (BC): Bomb calorimetry is a measure of energy loss in stool. This will be determined based on a 72-hour stool collection (Covance Labs, Madison, WI) performed on each subject before and after administration of pancreatic enzymes. All subjects will remain on their normal diet during stool collection. This includes the normal meals, snacks, and tube feeds that they typically receive. All samples will be collected at home, returned to CHOP, and frozen until the time of analysis. BC measures the heat of combustion of a reaction and in particular, measures the energy given off by a stool sample that is burned²⁸. As a result, it provides a measure of fecal energy loss in kcal/g stool. The energy loss from stool will be compared in each subject before and after administration of pancreatic enzymes.

Malabsorption blood test (MBT): This test will be performed on the MBT/CCK cohort only. These subjects will have the option to decline the MBT. The MBT is a measure of intestinal fat absorption and pharmacokinetic analyses yields primary outcomes from this test. The MBT involves consumption of an 8 ounce (oz) test meal that contains about 580 calories, 32.4 g of fat, and 50% calories from fat. Specifically, the fats contained in the test meal are pentadecanoic acid (PA), a free fatty acid, and triheptadecanoic acid (THA), a triglyceride with three molecules of heptadecanoic

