6.2 Secondary Endpoint

The **secondary aim** of this proposal is to assess the effect that administration of pancreatic enzymes will have on global absorption. Specifically, CNA and stool BC will be measured to detect changes in enteral protein absorption and stool energy losses, respectively, before and after administration of pancreatic enzymes.

An additional **secondary aim** includes that we will **explore** the ability of the MBT to detect changes in enteral fat absorption before and after administration of pancreatic enzymes in a subset of patients. This test will also help characterize the degree of pancreatic insufficiency in subjects.

A final **secondary aim** will **explore** if improved lipid digestion and release of free fatty acids due to pancreatic enzymes will promote intestinal adaptation by stimulating endocrine signaling. Specifically, GLP-2, IGF-1, IGFBP-3, and GH concentrations will be measured from blood samples before and after administration of pancreatic enzymes. CCK will also be measured in the MBT/CCK Cohort only before and after administration of pancreatic enzymes. Plasma citrulline will also be measured as a marker of intestinal adaptation before and after administration of pancreatic enzymes.

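### Bomb calorimetry is presented as a measure of absorption but analysed as stool energy loss alone, although energy intake is recorded in both periods

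*Combined protocol and SAP*

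**What the plan says.** The abstract at the front of the protocol (Study Interventions and Measures) puts BC on the same footing as the two absorption coefficients: "Enteral absorption will be measured using three methods: CFA, CNA, and BC". Section 1.5 lists it among the markers of absorption. Sections 2.2.1 and 6.2 place it under the secondary aim to "assess the effect that administration of pancreatic enzymes will have on global absorption", although both go on to give BC the narrower task of detecting changes in stool energy losses, as does H2.

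Section 5.2.2 defines the other two measures with intake in the calculation: "CFA % will be calculated based on determining the grams of fat consumed and the grams of fat excreted" and "CNA % will be calculated based on grams of nitrogen consumed and grams of nitrogen excreted". For BC it says only: "The energy loss from stool will be compared in each subject before and after administration of pancreatic enzymes". Section 6.3.1 (Efficacy Analysis) applies a paired t-test or Wilcoxon signed rank test with no intake term. Its exploratory comparison with the malabsorption blood test also uses BC as caloric loss in stool. Section 6.4 powers BC in kcal/day lost in stool.

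On diet, section 5.2.2 says: "All subjects will remain on their normal diet during stool collection". Nothing requires energy intake to match between the two periods. Section 3.2 states: "This is an open-label intervention therapeutic exploratory study, and not a randomized controlled trial". Section 5.1.3 provides for three-day weighed food records at baseline and on enzymes, with calories calculated from them.

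**The concern.** Stool energy loss depends on how much is eaten as well as on how much is absorbed. CFA and CNA account for intake by construction, and BC does not. In an uncontrolled comparison of two periods on a free diet, a mean difference in intake cannot be told apart from an enzyme effect by looking at stool output alone. A fall in stool kcal/day could mean that subjects ate less on treatment, and a real gain could be hidden if they ate more.

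The documents do not say that intake changes. Section 9.4.2 does list effects that could plausibly move it in either period: abdominal pain and vomiting among the known side effects of the product, and cramping after meals among the effects of stopping enzymes. The records needed to see such a shift are already planned, but no BC analysis uses them. What is at stake is the reading of BC as evidence on absorption.

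**Working it through.** **Inputs from section 6.4:** n = 22; planned fall 36 kcal/day (250 to 214); SD of differences 56; two-sided alpha 0.05; reported SBS fecal energy loss as high as 1609 kcal/day.

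**Assumed, not in the documents:** mean intake shifts g of 5% and 10%; stool loss proportional to intake unless stated; SD of differences unchanged at 56; analysis in kcal/day.

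**Step 1: the plan's own figure.** Power of the paired t-test comes from the noncentral t with 21 degrees of freedom and noncentrality d / 56 × √22. For d = 36 this is 36 / 56 × 4.690 = 3.015, and power is 0.820. The stated 80% with 22 subjects reproduces.

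**Step 2: effect of an intake shift.** With baseline loss 250 and on-treatment loss L at unchanged intake, the expected observed fall is d = 250 − L × (1 + g). L is 250 if absorption does not change and 214 if the planned effect is real.

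| True effect on absorption | Intake shift | Expected fall in stool kcal/day | Chance of a significant result |
|---|---|---|---|
| None | 0 | 0 | 0.05 |
| None | −5% | 250 − 250 × 0.95 = 12.5 | 0.17 |
| None | −10% | 250 − 250 × 0.90 = 25 | 0.52 |
| None, loss responds half as much | −10% | 250 × 0.05 = 12.5 | 0.17 |
| Planned 36 | 0 | 36 | 0.82 |
| Planned 36 | +5% | 250 − 214 × 1.05 = 25.3 | 0.52 |
| Planned 36 | +10% | 250 − 214 × 1.10 = 14.6 | 0.21 |

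**Step 3: scale.** A fall in intake of 36 / 250 = 14.4% would produce the whole planned change with no enzyme effect. A rise of 250 / 214 − 1 = 16.8% would cancel a true one. At the cited high-end loss the first figure is 36 / 1609 = 2.2%. The SD at that level would also be larger, so no test result is claimed there.

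**Step 4: does dividing by intake help?** Under proportional loss, with baseline intake I, a 10% fall gives 1 − (250 × 0.9) / (I × 0.9) = 1 − 250 / I, so percent absorption does not move. If loss responds only half as much, and I is assumed to be 2,000 kcal/day, the same fall takes percent absorption from 1 − 250 / 2000 = 87.5% to 1 − 237.5 / 1800 = 86.8%. That is a small apparent worsening, while stool kcal/day shows an apparent gain of 12.5.

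**The case against.** The strongest reply is that the operational text is consistent. H2 and sections 2.2.1, 5.2.2, 6.2, 6.3.1 and 6.4 all give BC the task of measuring stool energy loss, and the planned test does that. On this view the problem is loose wording in the abstract and background, and intake-based absorption is already covered by CFA and CNA. This stands in part: stool kcal/day is a proper endpoint for stool energy losses and should stay. It does not remove the explicit absorption label, or the placing of BC under the global-absorption aim.

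The bias is also hypothetical. It needs a systematic shift, since random variation in intake causes none. Usual meals and tube feeds, and the requirement in section 4.1 for typical food intake in the two weeks before Study Visit #1, limit drift. The effects in section 9.4.2 point to no clear net direction. All of this is fair, and the shifts above are assumptions. But limiting drift does not show that it is absent, and the weighed records can.

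The kcal/day figures depend on the unit. Section 5.2.2 gives kcal/g and section 6.4 kcal/day, while section 6.3.1 gives no unit for the paired test. If kcal/g were analysed, the step 2 figures would not apply. That also stands, and is a reason to write the conversion down.

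Finally, percent absorption is not a perfect measure, as step 4 shows, and diet-record error enters its denominator. The same error already enters CFA and CNA.

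**Conclusion.** The concern holds, as a minor point. BC is offered as evidence on absorption, yet no planned BC analysis uses the energy intake recorded in both periods. If loss is proportional to intake and the SD of differences is 56, an assumed 5% to 10% mean fall in intake raises the chance of a spurious BC finding from 5% to between 17% and 52%. A rise of the same size lowers power from 0.82 to between 0.52 and 0.21. Whether any shift occurs is unknown from the documents. The BC sample size is correct for stool loss, BC is secondary, and the primary CFA analysis is untouched, so the consequence is confined to how BC may be interpreted.

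**What to change.** In section 6.3.1, keep the paired comparison of stool energy loss in kcal/day as the powered BC analysis. Add a paired supportive analysis of percent energy absorption = 100 × (1 − stool kcal/day / enteral energy intake in kcal/day), with intake taken from the three-day weighed record and parenteral energy excluded. Report mean enteral intake in both periods. State that conclusions about absorption from BC rest on percent energy absorption read together with stool kcal/day, not on kcal/day alone.

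In section 5.2.2, state that kcal/day = kcal/g × total 72-hour stool weight in grams / 3.

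The cost is a short addition to section 6.3.1 and one sentence in section 5.2.2. Section 6.4 does not change, and no data are needed beyond the weight of the stool collection. The added measure has no stated power and cannot be given one from the documents, which supply neither energy intake nor the SD of its within-subject change. It should therefore be labelled supportive.

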5.3 Safety Evaluation

Safety will be monitored by adverse events reporting. The frequencies of AEs by type, body system, severity and relationship to study supplement will be summarized. SAEs (if any) will be described in detail.

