
MONITORING PLAN

The Principal Investigator, [name], is ultimately responsible for monitoring data integrity, patient safety, and overall study oversight. The study will be monitored weekly by the PI and [name]. The study protocol will be carried out in accordance with OHRP guidelines and requirements. SAEs that are unanticipated, serious, and possibly related to the study will be managed by the PI, [name], as well as her mentor ([name]). For subjects with SBS primarily managed at CHOP, members of the Intestinal Rehabilitation Program ([name]) will be consulted immediately for all SAEs. For subjects with SBS primarily managed at Penn Medicine/HUP, their primary gastroenterologist and co-investigator, [name], will be consulted immediately and will assume medical care. SAEs will be reported to the study sponsor, IRB, CTRC, and all members of the research team in accordance with requirements. Anticipated SAEs or those unrelated to the study will be reported to the same individuals/entities in accordance with requirements. There will be ongoing collection of data on adverse events and compliance to the treatment protocol throughout the study by the PI, [name], which will be reviewed weekly by [name].

SCHEDULE OF STUDY PROCEDURES & STUDY TIMELINE

Table 1. Summary of Study Visits #1 and #2 and Methods

	All subjects	MBT/CCK Subset		Non-MBT/CCK Subset		All subjects
		Visit 1	Visit 2	Visit 1	Visit 2	
Assessment	Visit 0					Visit 3
Obtain informed consent	•					
Study Intervention: Administration of Creon™			•		•	
Primary Outcome						
Coefficient of Fat Absorption (stool)		•	•	•	•	
Secondary Outcomes						
Coefficient of Nitrogen Absorption (stool)		•	•	•	•	
Fecal Bomb Calorimetry (stool)		•	•	•	•	
Malabsorption Blood Test (MBT) (PA, HA, HA/PA absorption, pharmacokinetics)		• [#]	• [#]			
Serum prealbumin		•	•	•	•	
Intestinal Adaptation: serum citrulline, IGF-1, IGF BP3, GLP 2, GH, stool pH, gastric pH		•	•	•	•	
Serum CCK		• [#]	• [#]			
Fecal elastase		•		•		
Diet						
24-hour dietary recall	•	• ^{**}				
3-day Weighed Food Record		•	•	•	•	
Safety						
Complete Blood Count with Differential		•	•	•	•	
Serum Basic Metabolic Panel		•	•	•	•	
Serum Hepatic Function Panel		•	•	•	•	
Adverse Event Monitoring		•	•	•	•	•
Other						
Anthropometry: height, weight, DXA, skinfolds, circumferences		•		•		
Nutrition Labs: serum vitamins A, E, K; 25-OH vitamin D; zinc; selenium; fatty acid profile	• [*]	•		•		
Health History and Medications		•		•		

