4.2 Study Treatment Phase

Subjects will have 2-4 visits in this study that will all occur at The Children's Hospital of Philadelphia. Study visit 0 will be to obtain informed consent and laboratories may be drawn (see description below). Study Visit #1 will be without pancreatic enzyme medication and Study Visit #2 will occur after they receive Creon™ as their pancreatic enzyme medication therapy. Study visit #3 will be off of study doses of pancreatic enzyme medication, though subjects on pancreatic enzymes at baseline may resume their regular dose. Study visit #3 will be to assess subject well-being, medication adherence, and to drop off stool collected and dietary records.

Study Visit #1 includes anthropometrics and baseline laboratories. A spot stool sample will be collected to determine stool pH. Subjects in the MBT/CCK cohort will have the MBT performed as well and a serum CCK concentration as part of their laboratories. Study Visit #2 includes repeat laboratories, which will not include micronutrient levels. A spot stool sample will be collected to determine stool pH. Subjects in the MBT/CCK cohort will again have the MBT performed and a serum CCK concentration drawn. (refer to study procedures in Table 1).

Study Visit 0: Visit for Consent and HIPAA Authorization for release of medical record information

- Informed Consent will be obtained at study visit 0. Subjects will have the option to complete this study visit via telephone. If subjects are taking pancreatic enzyme medication and will need to discontinue medication 3 days prior to Study Visit #1, a signed, informed consent form will be obtained in person or by mail, fax, or email prior to the beginning of any discontinuation of the medication. If subjects are taking a medication that directly alters fat absorption and will need to discontinue medication one week prior to Study Visit #1, a signed, informed consent form will be obtained prior to the beginning of any discontinuation of the medication. Medications that alter fat absorption will not be discontinued without the permission of the primary gastroenterologist. We will obtain a signed, informed consent form for all subjects in the MBT/CCK cohort prior to initiation of fasting or dietary changes for study visit 1. HIPAA Authorization forms from the subjects' institutions will be obtained and will be signed in person or obtained by mail/fax/email.

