4.4 Open-Label Treatment with Creon™

Subjects will receive open-label treatment with Creon™ as their pancreatic enzyme medication therapy and will receive this therapy for nine days encompassing Study Visit #2. There are two protocols for Study Visit #2. The first protocol is for subjects in the non-MBT/CCK cohort and the second protocol is for subjects in the MBT/CCK cohort. Please note that subjects who are eligible for the MBT/CCK subset and decline the MBT will follow the same protocol as the non-MBT/CCK subset.

Study Visit #2: Pancreatic Enzyme Medication Treatment Protocol for Subjects in the non-MBT/CCK Subset

Days 1 -4

- Pancreatic enzyme medication treatment
- Subject's normal diet

Day 5 – CHOP Visit to CTRC Outpatient Lab and NGL

- Subject's normal diet
- Pancreatic enzyme medication treatment

- Blood draw: pre-albumin, citrulline, IGF-1, IGF BP3, GLP-2, GH, CBC, CMP, hepatic function panel
- Spot stool sample will be collected for stool pH
- If subject has a G tube, spot gastric pH will be checked
- Adherence to pancreatic enzyme medication and Adverse Events Questionnaires
- Instructions will be given for collection and shipping for: stool collection (72-hour fecal fat, 72-hour fecal nitrogen, and bomb calorimetry), 3-day weighed food records, and adverse events diary

Day 6 - Home

- Pancreatic enzyme medication treatment
- Subject's normal diet
- Maintain adverse events diary

Day 7 - Home

- Pancreatic enzyme medication treatment
- Subject's normal diet
- 3-day weighed food records begins
- Food record – Day 1
- Maintain adverse events diary

Day 8 - Home

- Pancreatic enzyme medication treatment
- Subject's normal diet
- Food record – Day 2
- Stool collection (72-hour fecal fat, 72-hour fecal nitrogen, and bomb calorimetry), store frozen until brought to CHOP.
- 72-hour stool – Day 1
- Maintain adverse events diary

Day 9 - Home

- Pancreatic enzyme medication treatment
- Subject's normal diet
- Food record – Day 3
- 72-hour stool – Day 2
- Maintain adverse events diary

Day 10 - Home

- Pancreatic enzyme medication treatment

- Subject's normal diet
- 72-hour stool – Day 3
- Maintain adverse events diary

Day 11 - Home

- Subjects who had discontinued a medication that directly alters fat absorption for this study can resume this medication as it was prescribed by their primary physician

Study Visit #2: Pancreatic Enzyme Medication Treatment Protocol for Subjects in the MBT/CCK Subset

Days 1, 2, & 3

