5.1.2 Laboratory Evaluations

Serum 25-dihydroxyvitamin D and pre-albumin will be assessed at CHOP laboratories. PIVKA II ([name], Tuft's University, Medford, MA) and/or undercarboxylated osteocalcin % (UCOC %) will be assessed for vitamin K status ([name], Yale University, New Haven, CT). Prealbumin, zinc, serum retinol (vitamin A), α tocopherol (vitamin E), and selenium will be assessed at CHOP Laboratories using standard techniques. A fatty acid profile will be assessed by Mayo Medical Laboratories (Rochester, MN). This will provide data on baseline malabsorption and nutritional

status resulting from short bowel syndrome that may be improved with pancreatic enzyme medication in subjects. Safety measures include results from serum basic metabolic panel (BMP), hepatic function panel, and complete blood count with differential (CBC) performed at CHOP Laboratories using standard techniques. The hepatic function panel will provide serum albumin, total protein, bilirubin, and liver enzymes to provide additional liver and nutritional status information. Serum citrulline, IGF-1, IGF BP3, GLP-2, GH, and CCK levels (MBT/CCK subset only) will be assessed by the CTRC Core Laboratory at CHOP. All individuals from institutions outside of CHOP will receive only coded, not readily identifiable, samples for analyses and are not otherwise engaged in human subjects' research.

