6.3.1 Safety Analysis

Safety will be monitored by adverse events reporting. The frequencies of AEs by type, body system, severity and relationship to study supplement will be summarized. SAEs (if any) will be described in detail.

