8.3 Definition of an Adverse Event

An adverse event is any untoward medical occurrence in a subject who has participated in the research protocol. The occurrence does not necessarily have to have a causal relationship with the research activities. An AE can therefore be any unfavorable or unintended sign (including an abnormal laboratory finding, for example), symptom, or disease temporally associated with the use of a medicinal product, whether or not considered related to the research activities.

All AEs (including serious AEs) will be noted in the study records and on the case report form with a full description including the nature, date and time of onset, determination of non-serious versus serious, intensity (mild, moderate, severe), duration, causality, and outcome of the event.

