9.4.2 Risk Assessment

The most common side effects associated with taking the pancreatic enzyme Creon™ in clinical trials were abdominal pain, hyperglycemia, hypoglycemia, frequent abnormal bowel movements, flatulence, vomiting, dizziness, sore throat and cough. Irritation of the inside of the mouth may occur if Creon™ is not swallowed completely. Additionally, subjects in diapers are at risk of diaper dermatitis due to Creon™ if diapers are not changed frequently and a heavy barrier cream is not utilized. Increase in blood uric acid levels (hyperuricemia), and severe allergic reactions (pork allergy) including trouble with breathing, skin rashes or swollen lips, although rare, may occur. Although it has never been reported, it is possible for a person to get a viral infection from taking pancreatic enzyme products that come from pigs. Fibrosing colonopathy and colonic strictures is a rare, serious adverse reaction associated with chronic high-dose pancreatic enzyme use over a prolonged period of time with enzyme doses in excess of 6,000 LU/kg body weight per meal or 10,000 LU/kg/day in patients with cystic fibrosis. Doses of Creon™ prescribed for this study will not exceed 10,000 LU/kg/day or 4000 LU/grams of fat/day for any subject.

There are risks associated with discontinuing pancreatic enzyme medication for subjects with SBS who have noted clinical improvement on pancreatic enzymes. These include feelings of indigestion, stomach cramping after meals, gas, foul smelling, floating stools, light-colored, orange or yellow stools, frequent or loose stools, or weight loss. Some participants in the study may be at increased risk for these symptoms.

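### Safety blood panels are drawn off enzyme and on Creon, but the safety analysis plans no summary of them, so laboratory changes may be missed or hard to separate from abnormalities already present

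*Combined protocol and SAP*

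**What the plan says.** The safety analysis is stated three times in the same terms: in the synopsis (Safety Evaluations), in 5.3 and in 6.3.1 Safety Analysis. Each opens with "Safety will be monitored by adverse events reporting", goes on to "The frequencies of AEs by type, body system, severity and relationship to study supplement will be summarized", and adds that serious events will be described in detail. None mentions laboratory values.

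The plan also collects laboratory data for safety. Section 5.1.2 says "Safety measures include results from serum basic metabolic panel (BMP), hepatic function panel, and complete blood count with differential (CBC"). Table 1 lists these panels ("Serum Basic Metabolic Panel" among them) in its Safety block at Visits 1 and 2 for both subsets. The two visits differ in exposure: "Study Visit #1 will be without pancreatic enzyme medication and Study Visit #2 will occur after they receive Creon" (4.2). The on-treatment draw for the non-MBT protocol reads "Blood draw: pre-albumin, citrulline, IGF-1, IGF BP3, GLP-2, GH, CBC, CMP, hepatic function panel" (4.4), and the MBT list contains the same three panels.

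Section 9.4.2 states: "The most common side effects associated with taking the pancreatic enzyme Creon™ in clinical trials were abdominal pain, hyperglycemia, hypoglycemia", followed by other effects. Section 8.3 gives laboratory values a way into the adverse-event data: "An AE can therefore be any unfavorable or unintended sign (including an abnormal laboratory finding, for example").

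**The concern.** The panels form paired off-enzyme and on-Creon data in every subject, and glucose change is a named effect of the product. The stated analysis uses them only if someone records an abnormal value as an adverse event.

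Two things are lost. A shift that stays within the reference range is not an abnormal finding and so is never tabulated. And where a value is out of range, no rule says how it is set against that subject's Visit 1 result. This matters here because section 1.1 lists glucose instability and cholestatic liver disease among the complications of central access and parenteral nutrition. The named drug effect overlaps a known background problem.

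At stake is the completeness of the safety report for a study in which 16 of the 26 planned subjects are children and 7.1.3 prefers the highest doses considered safe. Efficacy conclusions are not affected.

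**Working it through.** **Step 1: is a laboratory summary planned anywhere else?**
- 6.3 (general methods) plans descriptive statistics for the study sample. It names neither the safety panels nor change between visits.
- 6.3.1 Efficacy Analysis limits paired comparisons to CFA, CNA, BC, the MBT parameters and the H4 hormones.
- 5.1.3 has subjects asked about adverse events and asked to rate their intensity. No laboratory grading scale is given.
- 8.3 gives no cut-off and no comparison with Visit 1.

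So no section plans a Visit 1 to Visit 2 summary of the panels. If all 26 subjects complete both visits, 26 × 2 = 52 sets of safety bloods have no planned summary.

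**Step 2: the plan's own paired figure.** The documents give no sizing for safety laboratories. The nearest figure is the CFA power statement in 6.4: n = 22, difference 9, SD of differences 14, two-sided α = 0.05, paired t-test, 80% power. The noncentrality is (9/14) × √22 = 3.02, and the exact noncentral-t power is 0.820. The statement reproduces, so 22 pairs is a sound basis for the next step.

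**Step 3: precision of a descriptive paired summary.** The 95% CI half-width, in units of the SD of the within-subject change, is t(0.975, n−1)/√n.

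| Data set | n | Half-width |
|---|---|---|
| All evaluable pairs (3.3.2) | 22 | 2.080/√22 = 0.44 SD |
| All enrolled | 26 | 2.060/√26 = 0.40 SD |
| Fasted glucose, MBT protocol | 10 | 2.262/√10 = 0.72 SD |
| Normal-diet glucose, non-MBT protocol | 16 | 2.131/√16 = 0.53 SD |

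Glucose needs the split because MBT subjects fast from 8 pm before the draw, while non-MBT subjects eat normally. The last two rows assume that no adult declines the MBT and that nobody drops out. An adult who declines moves to the non-MBT protocol.

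**Step 4: can a count of new abnormal values miss a group shift?** The documents give no laboratory means or SDs, so these inputs are assumed: values standardized to SD 1, upper limit at +1.96 SD, within-subject correlation 0.3 to 0.7, n = 22. With p the probability of being in range at Visit 1 and above the limit at Visit 2, the chance of no new high value is (1 − p)^22.

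| Assumed mean shift | Chance of no new high value | Power of a paired comparison |
|---|---|---|
| 0.3 SD | 37% to 44% | 21% to 41% |
| 0.5 SD | 22% to 27% | 47% to 82% |
| 0.7 SD | 11% to 14% | 75% to 98% |

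A real shift can thus leave no new out-of-range value. The powers show what the paired data hold for an analyte pooled over 22 subjects; they would be lower for glucose after the split. This is not a proposal for formal testing.

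**The case against.** The best defence is section 8.3. An abnormal laboratory finding can be an adverse event whether or not it is thought related to the research, and each event is recorded with onset, duration, causality and outcome. A value already abnormal at Visit 1, if recorded, can be dated before the first Creon dose. Events are also sought through diaries, questionnaires and weekly review. This is a small, exploratory, single-arm study of about ten days of an approved product, and safety is not among its stated aims. All of that stands. It limits the point to in-range shifts and to the lack of a written cut-off or Visit 1 rule.

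A reader might infer more, and the documents do not support it:
- **That the bicarbonate and potassium thresholds in 9.4.2 would go unreported.** They concern the high-fat MBT meal, offered to about ten adults, and are not presented as Creon signals in children. Subjects who meet them are to be hospitalized. That makes the event serious under 8.4, to be described in detail under 6.3.1 Safety Analysis.
- **That abnormal values attributed to parenteral nutrition drop out.** Section 8.3 counts events regardless of relationship.
- **That pre-existing abnormalities will inflate a count at Visit 2.** The plan does not count raw Visit 2 abnormalities, and the documents give no prevalence from which to size such an effect.

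It is also fair that splitting glucose by fasting state leaves wide intervals, and that a single glucose value per visit is weak evidence of a drug effect.

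**Conclusion.** The point holds as a gap in safety reporting. Followed as written, the plan would not report in-range changes in its own designated safety panels, and it does not say how an abnormal value relates to the same subject's off-enzyme value. Changes on Creon may be missed or be hard to separate from what was already there; nothing shows that they will be.

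The attainable precision is modest: a half-width of 0.44 SD of the change for 22 pairs, and about 0.72 SD and 0.53 SD for the two glucose groups before attrition. The chances of seeing no new abnormal value rest on assumed standardized inputs and serve as illustration only. Without a control group, any shift is descriptive and cannot be attributed to Creon. The sample size and the primary CFA analysis are unaffected.

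**What to change.** Add to 6.3.1 Safety Analysis, and align 5.3 and the synopsis:

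1. A descriptive summary of the panels already drawn, at least for glucose and electrolytes: Visit 1 to Visit 2 shift tables (low, normal, high, by age- and sex-specific laboratory ranges) and within-subject change with 95% CI.
2. Glucose shown separately for fasted (MBT) and normal-diet draws, with a note on the wider intervals.
3. Prior enzyme users flagged, since their Visit 1 draw follows a three-day washout.
4. A statement that Visit 2 values reflect day 5 of ten Creon days, as the day lists in 4.4 and the text of 7.1.3 have it, and that shifts are descriptive without a control group. Tables 3 and 4 place Visit 2 on treatment day 4, and the opening of 4.4 speaks of nine days; these passages must be reconciled first.
5. In the tabulation only, laboratory adverse events marked as new or worsened, or as present at Visit 1. The rules for recording adverse events and reporting serious ones stay unchanged.
6. Table 1 and 5.1.2 (BMP) reconciled with the visit lists in 4.2 and 4.4 (CMP), so that the analyte list is fixed.

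The cost is a paragraph of analysis text and two tables, with no new samples or visits. The downside is more rows to report, with small numbers in each.
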